5. SAMPLE SIZE CONSIDERATIONS

Recruitment goals for the 510(k) phase of the study are at least 100 specimens positive for each of CT and TV, and at least 45 specimens positive for NG as determined by PIS. Recruitment goals for the CLIA waiver phase of the study are 120 positive specimens for each of CT, TV, and 45 NG. Approximately 585 subjects will be recruited from low-prevalence sites (one third of the 1,750) and approximately 1165 subjects will be recruited from high prevalence sites. The average expected proportion of samples positive via PIS for CT, TV, and NG among subjects enrolled at the high prevalence sites are, respectively, 12.4%, 19.5%, and 8.1%. The corresponding estimates for the low prevalence sites are 1.7%, 1.0%, and 1.4%. Based on these prevalence estimates, it is expected that the enrollment targets will be met for the three organisms. Thus, the study as designed is expected to meet the 510(k) and CLIA waiver recruitment goals for all three organisms. If NG prevalence is lower than expected, banked NG+ samples may need to be leveraged to meet the recruitment goals for NG. As indeterminate PIS designations or invalid or failed Click device results are expected for a small number of cases, enrollment may extend beyond 1750 to replace these results. The duration of enrollment may be extended if the actual prevalence of any of the organisms is lower than predicted.

For the estimation of the sensitivity and specificity of the Click device, we assume both the sensitivity and specificity is at least 95%. For 510(k) clearance, the study aims to demonstrate that sensitivity to each of CT and NG is at least 95% with a lower bound of the two-sided 95% Wilson Score confidence intervals at least 90%, and to demonstrate that sensitivity to TV is at least 95% with a lower bound of the two-sided 95% Wilson Score confidence intervals at least 85%. Regarding specificity, the study aims to demonstrate specificity to each of CT, TV, and NG is at least 95% with a lower bound of the two-sided 95% Wilson Score confidence intervals at least 90%. For the CLIA waiver, the study aims to demonstrate that both the sensitivity and specificity to each of CT, TV, and NG is at least 95% with a lower bound of the two-sided 95% Wilson Score confidence intervals at least 89%.

To demonstrate this for CT and TV, 95% Wilson Score confidence intervals were calculated for a range of sample sizes, number of PIS-positive samples, and sensitivity/specificity estimates. Given the uncertainty in the exact number of subjects enrolled or PIS-positive samples, the following parameter ranges were explored: total sample sizes of 1500 to 2000, 100 to 200 PIS-positive samples, and sensitivity/specificity estimates of 95% to 99%. Wilson Score confidence intervals were calculated for each combination of sample size, number of PIS-positive samples, and sensitivity/specificity. As an example, [Table 2](#) below displays the lower confidence bound using a sample size of 1750 and a select subset of the number of PIS-positive samples.

Table 2: Lower 95% Wilson Score Confidence Bounds (%) for Various Number of PIS-Positive Samples and Sensitivity and Specificity Values

Number of PIS-Positive Samples	Sensitivity (%)					Specificity (%)				
	95	96	97	98	99	95	96	97	98	99
100	88.8	90.2	91.5	93.0	94.6	93.9	94.9	96.1	97.2	98.4
101	88.9	90.3	91.6	93.1	94.6	93.9	95.0	96.1	97.3	98.4
102	89.0	90.3	91.7	93.1	94.7	93.9	95.0	96.1	97.3	98.4
103	89.1	90.4	91.8	93.2	94.7	93.9	95.0	96.1	97.3	98.4
104	89.2	90.5	91.9	93.3	94.8	93.9	95.0	96.1	97.3	98.4
105	89.3	90.6	91.9	93.3	94.8	93.9	95.0	96.1	97.3	98.4
106	89.4	90.7	92.0	93.4	94.8	93.9	95.0	96.1	97.3	98.4
120	89.5	91.7	92.9	94.1	95.4	93.9	94.9	96.1	97.2	98.4
121	89.6	91.8	93.0	94.2	95.5	93.9	94.9	96.1	97.2	98.4
122	89.7	91.9	93.0	94.2	95.5	93.9	94.9	96.1	97.2	98.4
123	89.8	91.9	93.1	94.3	95.5	93.9	94.9	96.1	97.2	98.4
124	89.8	92.0	93.1	94.3	95.6	93.9	94.9	96.1	97.2	98.4
125	89.9	91.0	93.2	94.4	95.6	93.8	94.9	96.1	97.2	98.4
126	90.0	91.0	93.2	94.4	95.6	93.8	95.0	96.1	97.2	98.4

Over the entire ranges of parameter values explored, the lower bound of the specificity confidence interval never fell below 93.6%. The lower bound of the sensitivity confidence intervals never fell below 88.8% and was greater than or equal to 89% for all combinations of parameter values except for the following scenario:

- Sample Size = Any, Number of PIS-positive samples = 100 or 101, Sensitivity = 95%

The lower bound of the sensitivity confidence intervals was greater than or equal to 90% for all combinations of parameter values except for the following scenarios:

- Sample Size = Any, Number of PIS-positive samples = 100 to 112, Sensitivity = 95%
- Sample Size = Any, Number of PIS-positive samples = 120 to 126, Sensitivity = 95%

Thus, apart from a few scenarios, assuming the sensitivity/specificity of the Click device is at least 95%, the study as planned should be able to meet the confidence interval estimate requirements for 510(k) clearance and CLIA waiver for CT and TV.

For NG, the minimum number of PIS-positive samples required for the 510(k) and CLIA Waiver reports is 45. The planned maximum sample size for NG-positive samples is 85. Due to the small 510(k) and CLIA Waiver enrollment targets for NG and the difficulty in recruiting NG-positive subjects, reviews of the sensitivity of the Click device with regard to NG detection will occur during the course of the study; see Section 6.5.

6. GENERAL STATISTICAL CONSIDERATIONS

6.1. General Principles

Tabulations will be used extensively to summarize the data. All continuous variables will be summarized using the following descriptive statistics: n (sample size), mean, standard deviation, median, maximum, and minimum. The frequency and percentages (based on the sample size) of observed levels will be reported for all categorical measures. Wilson confidence intervals (CIs) for binomial proportions and differences in binomial proportions will be computed for product performance variables (e.g. sensitivity and specificity). A 5% two-sided significance level will be used; i.e. two-sided 95% confidence intervals will be generated.

All summary tables will include the total population size relevant to that table/column. If applicable and/or appropriate, missing observations will be displayed in the tables.

Note that in the data listings, Subject ID is the unique subject identifier, not the Study ID used on study, and additionally, dates will not be included.

6.2. Analysis Populations

6.2.1. Enrolled Population

The Enrolled population will include all participants enrolled.

6.2.2. Evaluable Population

The Evaluable analysis population will include all subjects enrolled with a valid Click result and a valid PIS designation. There will be a separate Evaluable population for each organism. A subject will be excluded from the organism-specific evaluable population if any of the following criteria are met:

- Either the Click result is invalid or the PIS designation is indeterminate
- The specimen for either the Click or comparator assays is missing or untested
- The specimen for the Click device was tested more than 2 hours after collection
- The specimen for the comparator assay was tested outside the stability window
- Subject did not meet eligibility criteria
- Any protocol deviation that, in the opinion of the investigators, is deemed to impact validity of assay results
- Any other reason that, in the opinion of the investigators, is deemed to impact validity of assay results (e.g. receipt of a concomitant medication that could interfere with assay results)

See Section [3.3.2](#) for definitions of valid result and designation.

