2.1.2 Reference Method

The Patient Infected Status (PIS) provides the reference for this study. This algorithm incorporates results from three recognized FDA-cleared methods for the CT and NG pathogens and from three recognized FDA-cleared methods for TV (Table 1). NAAT 1, NAAT 2, and NAAT 3 refer to BD ProbeTec, Hologic Aptima, and BD MAX, respectively.

BD ProbeTec™ CT/GC Qx Amplified DNA Assays – BD Molecular Diagnostics
BD ProbeTec™ Trichomonas vaginalis Qx Assay – BD Molecular Diagnostics
APTIMA COMBO 2 Assay – Hologic, Inc.
APTIMA Trichomonas Vaginalis Assay – Hologic, Inc.
BD MAX™ CT/GC/TV – BD Molecular Diagnostics

Table 1: PIS Algorithm

	NAAT1	Positive				Negative				Equivocal (EQ)*			
	NAAT2	POS	EQ	NEG	INVALID	POS	EQ	NEG	INVALID	POS	EQ	NEG	INVALID
NAAT3													
POS		NA ^a	POS	POS	POS	POS	IND	NA	IND	POS	IND	IND	NA
NEG		NA	IND ^b	NEG	IND	NEG	NEG	NA	NEG	IND	IND	NEG	NA
UNR ^c		NA	IND	IND	IND	IND	IND	NA	IND	IND	IND	IND	NA
INVALID ^d		NA	IND	IND	IND	IND	IND	NA	IND	IND	IND	IND	NA

^aNA = not applicable and indicates that no tie-breaker test is required because the first two reference tests were in agreement.

^bIND = indeterminate and indicates that the true patient status cannot be determined based on the results obtained from the three reference tests.

^cUNR = unresolved.

^dFor the BD MAX CT/GC/TV assay (NAAT 3), indeterminate and incomplete test results as reported by the instrument should be interpreted as INVALID using this composite comparator algorithm.

The diagnostic variable of interest for this study is the binary infected/not infected findings for CT, NG, and TV on the Click Diagnostics Sexual Health Test as compared to PIS determined by existing comparator tests. The designation of a subject as being positive, negative, or indeterminate will be based on the combined results of the reference assay tests. A subject will be considered “Positive” where two reference assays are positive. A subject will be considered “Negative” where two reference assays are negative. If the results of the first two assays are discordant, the PIS will be determined by the third assay (tie-breaker). Any other potential combination of results will be considered an “Indeterminate” result. The testing methods utilized in the study are summarized in Table 2.

Table 2: Organism Type Testing Methods

Organism	Self-Collected/ Click Device	HCP-Collected/Comparator Methods		

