7.4.1 Analysis Populations

The following analysis populations will be defined separately for each report (Interim, 510(k), CLIA Waiver). The statistical analysis plan will include the further details on the definitions of the report-specific analysis populations.

Enrolled Population: This population includes all participants enrolled at the time of the data cut-off for the report.

Evaluable Population: This population includes all samples available at the time of the data cut-off for the report, which provide an evaluable Click Diagnostics Sexual Health Test result and an evaluable PIS result for each tested pathogen (CT, NG, TV). There will be a separate Evaluable population for each organism.

A sample provides an evaluable result if both the Click device and the PIS provide a valid positive or negative result.

The primary outcome measure of sensitivity and specificity of the Click Diagnostics Sexual Health Test will be evaluated in the evaluable population.

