3.3. Study Definitions and Derived Variables

3.3.1. Patient Infected Status

The Patient Infected Status (PIS) is a ternary variable (Positive/Negative/Indeterminate) calculated via an algorithm incorporating results from the three comparators assays. A PIS designation is derived for each specimen and organism.

For each organism, the specimen will first be tested using the BD Probtec and Hologic Aptima assays.

If the result of both assays is Positive, then the PIS designation will be Positive.

If the result of both assays is Negative, then the PIS designation will be Negative.

If the result of both assays is Equivocal, then the PIS designation will be Indeterminate.

If the result of both assays is Invalid, then the PIS designation will be Indeterminate.

If the results of the assays are discordant, then the BD MAX assay will be used as a tie-breaker. [Table 1](#) below presents the possible combinations of results of the three assays and the corresponding PIS designation for each combination.

Table 1: PIS Designations when Tie-Breaker Assay is used

BD Probtec Result	Hologic Aptima Result	BD Max Result	PIS Designation
Positive	Equivocal	Positive	Positive
		Negative	Indeterminate
		Unresolved or Invalid	Indeterminate
	Negative	Positive	Positive
		Negative	Negative
		Unresolved or Invalid	Indeterminate
	Invalid	Positive	Positive
		Negative	Indeterminate
		Unresolved or Invalid	Indeterminate
Negative	Positive	Positive	Positive
		Negative	Negative
		Unresolved or Invalid	Indeterminate
	Equivocal	Positive	Indeterminate
		Negative	Negative
		Unresolved or Invalid	Indeterminate
	Invalid	Positive	Indeterminate
		Negative	Negative
		Unresolved or Invalid	Indeterminate
Equivocal	Positive	Positive	Positive
		Negative	Indeterminate
		Unresolved or Invalid	Indeterminate
	Negative	Positive	Indeterminate
		Negative	Negative
		Unresolved or Invalid	Indeterminate
	Invalid	Positive	Indeterminate
		Negative	Indeterminate
		Unresolved or Invalid	Indeterminate
Invalid/Missing	Positive	Positive	Positive
		Negative	Indeterminate
		Unresolved or Invalid	Indeterminate
	Equivocal	Positive	Indeterminate
		Negative	Indeterminate
		Unresolved or Invalid	Indeterminate
	Negative	Positive	Indeterminate
		Negative	Negative
		Unresolved or Invalid	Indeterminate

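### SAP 6.2.2 excludes subjects for any missing or untested comparator specimen, including one not needed for the PIS, so subjects with a valid PIS can be dropped from the primary population

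*SAP*

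**What the plan says.** SAP 6.2.2 opens with a positive definition: "The Evaluable analysis population will include all subjects enrolled with a valid Click result and a valid PIS designation". It then lists criteria, any one of which excludes a subject from the organism-specific population. The first removes an invalid Click result or an indeterminate PIS. The second is "The specimen for either the Click or comparator assays is missing or untested", with no qualifier.

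The reference algorithm does not need all three comparators. SAP 3.3.1 runs ProbeTec and Aptima first and adds: "If the results of the assays are discordant, then the BD MAX assay will be used as a tie-breaker". The footnote to Protocol Table 1 explains that its NA entry "indicates that no tie-breaker test is required because the first two reference tests were in agreement". SAP Table 1 also has a block for ProbeTec labelled "Invalid/Missing", which yields Positive when Aptima and BD MAX are both positive and Negative when both are negative.

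Protocol 7.4.1 states: "A sample provides an evaluable result if both the Click device and the PIS provide a valid positive or negative result". SAP section 12 reports no departure from the protocol's analyses.

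**The concern.** The opening sentence and the first criterion already confine the population to subjects with a valid PIS. The comparator part of the second criterion can therefore remove only subjects whose PIS is valid. The SAP classifies these women in one section and discards them in another.

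Swabs that are not collected or not tested are foreseen: the protocol deviation shell (SAP Table 21) has a row for each. Two programmers working from 6.2.2, Table 1 and the shells could build different primary populations, and the choice could fall after results are visible, because device performance is tracked throughout the study (Protocol 7.3.1, SAP 6.5).

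**Working it through.** **1. The texts compared.** All cases assume a valid Click result and no other exclusion.

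| Case | PIS under SAP 3.3.1 | Opening of 6.2.2 and Protocol 7.4.1 | Second criterion of 6.2.2 |
|---|---|---|---|
| ProbeTec missing, Aptima + and BD MAX + | Positive | In | Out |
| ProbeTec missing, Aptima − and BD MAX − | Negative | In | Out |
| ProbeTec and Aptima agree (+ or −), BD MAX swab missing | Positive or Negative | In | Out |
| ProbeTec missing, any other Aptima/BD MAX pair in that block | Indeterminate | Out | Out (already out under the first criterion) |

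Of the nine rows in the missing-ProbeTec block, two give a valid PIS. The first three lines of the comparison are the conflict. The fourth shows that the comparator wording adds nothing where the PIS cannot be determined.

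**2. What the shells imply.** The Table 5 shell words this exclusion as missing or untested for Click or for the PIS, not for each assay. The Table 27 shell uses the Evaluable population as its denominator, and its first example row for each organism has ProbeTec and Aptima positive, BD MAX NA and PIS Positive.

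**3. Reproducing the plan's figures.** Two-sided 95% Wilson lower bound, with p = x/n and z = 1.96:

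L = [p + z²/(2n) − z·√(p(1−p)/n + z²/(4n²))] / (1 + z²/n)

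- 95/100 gives 88.8% and 114/120 gives 89.5% (SAP Table 2: 88.8 and 89.5).
- 45/45 gives 92.1% and 44/45 gives 88.4% (Protocol Table 4: 92.1 and 88.4).

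**4. Expected positives at N = 1750** (SAP section 5: 1165 high-prevalence and 585 low-prevalence subjects).

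- CT: 1165 × 0.124 + 585 × 0.017 = 154.4
- TV: 1165 × 0.195 + 585 × 0.010 = 233.0
- NG: 1165 × 0.081 + 585 × 0.014 = 102.6

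**5. Possible loss.** The documents give no rate for a missing comparator specimen that the PIS did not need. The rates below are assumptions, applied equally to positives and negatives.

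| Assumed rate | Subjects lost | CT+ lost | TV+ lost | NG+ lost |
|---|---|---|---|---|
| 0.5% | 8.75 | 0.8 | 1.2 | 0.5 |
| 1% | 17.5 | 1.5 | 2.3 | 1.0 |
| 2% | 35 | 3.1 | 4.7 | 2.1 |
| 5% | 87.5 | 7.7 | 11.7 | 5.1 |

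At 5%, 146.7 CT, 221.4 TV and 97.4 NG positives remain, against CLIA waiver goals of 120, 120 and 45.

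**6. One subject at NG's first review.** Suppose there are 46 PIS-positive NG subjects with one Click false negative, and one of the 46 lacks an unneeded comparator swab.

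- All kept: 45/46, p = 0.97826. The numerator is 0.97826 + 0.04176 − 0.05933 = 0.96069 and the denominator is 1.08351, so L = 88.7%. This misses both the 90% (510(k)) and the 89% (CLIA waiver) limits.
- The false negative is the subject dropped: 45/45, L = 92.1%. This meets both.
- A true positive is dropped instead: 44/45, L = 88.4%, slightly lower than with all kept.

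**The case against.** A reader might infer that the second criterion excludes every subject whose first two assays agree, because her BD MAX specimen is untested by design. Only tie-broken subjects would then remain: at an assumed 1% to 10% discordance, about 18 to 175 of 1750, with about 1 to 10 NG positives. The documents do not support this as the intended rule. The Table 27 denominator, the Table 5 wording and the opening sentence of 6.2.2 all treat concordant subjects without a BD MAX run as evaluable, and Listing 12 codes NA apart from an unresolved or invalid BD MAX result. Mass exclusion shows only that the wording is defective; it is not an expected loss.

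Protocol 7.4.1 also leaves further detail of the populations to the SAP, so an added exclusion is not an error in itself. That stands for ordinary data-quality exclusions. It does not remove the conflict inside the SAP between 6.2.2 and Table 1.

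A reader might extend the point to the criterion "The specimen for the comparator assay was tested outside the stability window". Excluding such subjects is a defensible, prespecified quality rule, and treating the result as missing would be an alternative to it, not a correction. Nor is the absence of a missing label for BD MAX an error: Protocol 2.1.2 already sends any combination not otherwise covered to indeterminate.

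On size, the rates are assumed, expected positives exceed every goal, and Protocol 7.2 and SAP section 5 allow enrollment to be extended. Nothing links an unneeded missing swab to a Click miss, so the NG example shows what can happen, not what is likely. Exclusions will also be visible by reason in Table 5 and by subject in Listing 2. All of this stands.

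**Conclusion.** The second criterion of SAP 6.2.2 is wrong as written. It excludes subjects to whom the SAP itself assigns a valid PIS, in two situations: ProbeTec missing with Aptima and BD MAX in agreement, and the BD MAX swab missing with ProbeTec and Aptima in agreement. The first is explicit in SAP Table 1. The second follows from BD MAX being only a tie-breaker.

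The loss is probably small, and no enrollment target is at risk even at the assumed 5%. It matters because the rule defines the population for the primary estimates, and because with 45 or so NG positives one subject can move the lower bound across both acceptance limits (88.7% against 92.1%), if that subject happens to be the only false negative.

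**What to change.** Reword the second criterion of SAP 6.2.2 along these lines: *the Click specimen is missing or untested, or a comparator specimen required to determine the PIS is missing or untested so that the PIS is indeterminate*. Equivalently, delete the comparator part and rely on the first criterion. Give the matching row of the Table 5 shell the same wording.

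The cost is a SAP text edit made before database lock, with no extra data, testing or subjects. Changing the stability-window criterion, or adding a missing label for BD MAX in SAP Table 1, is optional and not needed to correct this error.

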6.3. Covariates, Center Effects, and Subgroups

Though the study is not designed to adequately assess product performance within subgroups, certain summaries will be presented by operator, clinical site, lot, and symptomatic status (see Section [8.2](#)).

Safety and product performance data will be both broken up and pooled across clinical sites and operators within clinical site. Though Click devices are manufactured and shipped centrally from Click Diagnostics, the sites are using standardized procedures for assessment of unsolicited adverse events, the study utilizes a

central laboratory for comparator testing, and the study is not designed to detect subgroup effects, operator and center effects are possible. See Section 8 and Section 9 for more details.

As necessary, the study Sponsor, their designated Statistics and Data Coordinating Center, and/or authorized Principal Investigators may perform additional analyses depending on the nature of the data acquired, new regulatory directives, or to respond to unforeseen contingencies during the course of the study. Such analyses and their results, including a rationale for performing said analyses, will be described in detail in the study report and/or study publication.

6.4. Multiple Comparisons/Multiplicity

No adjustments for multiplicity are planned.

6.5. Timing of Analysis, Interim Analyses and Data Monitoring

The final analysis will be performed after database lock when all subjects have their data entered and monitored.

In addition, the primary analysis of agreement between the Click device results and PIS will be performed on an ongoing basis during the course of the study. These analyses will track performance of the investigative device and thereby serve to inform the Sponsor team and Click Diagnostics as to the likelihood of successful completion of the study with performance conforming to acceptance criteria, or conversely, to eventual futility of the study for failure to achieve acceptable performance. In no case shall the results of these ongoing analyses initiate an early termination of the study for benefit, i.e. based upon early achievement of acceptable performance.

In accord with DMID Policy, analysis results shall be distributed only to the Sponsor team and to Click Diagnostics and the receiving personnel shall not further distribute the results. No results shall be supplied to study site personnel or to study monitors, and neither the raw data nor the analysis of these ongoing analyses shall be submitted to FDA. The results of these ongoing analyses shall not translate into study design changes, protocol amendments, or investigative device design changes. The ongoing performance tracking is outside the scope of this SAP.

